More broadly, this study established the safety and feasibility of modulating intrinsic network activity with non-invasive brain stimulation. [name] (advisor) group has corroborated this by recently showing that active transcranial direct current stimulation (tDCS) to DLPFC decreases DN synchrony, but increases connectivity in an anticorrelated network.⁴⁹ Other research groups have published consistent results⁵⁰: Keeser et al. showed that anodal stimulation of DLPFC with tDCS modulated connectivity in the DN⁵¹; Alon et al. found that excitatory stimulation of M1 with tDCS decreased intrinsic connectivity between bilateral M1.⁵²

Nevertheless, further exploration of intrinsic network dynamics using rTMS and fMRI would benefit from a greater understanding of the physiologic effects of rTMS upon the directly targeted brain region. In our preliminary study, connectivity changes may have been predominantly determined by stimulation dependent changes in excitability at lPpL. While prior studies suggest that high and low frequency rTMS exert opposing effects on cortical excitability⁵³⁻⁵⁵, we could not verify the magnitude, directionality or diffusivity of the stimulation at lPpL. Another consideration is that tonic activity at lPpL or at distal network nodes, might constrain the extent to which connectivity is modulated with rTMS.⁵⁶ This is especially germane to MDD, given the presence of baseline metabolic derangements at DLPFC and sgACC. An ideal way to circumvent this shortcoming is to simultaneously accrue information about changes in local nodal activity *and* changes in network connectivity.

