II. SPECIFIC AIMS

Aim 1: To assess rTMS induced changes in functional connectivity in cortico-limbic networks

Hypothesis 1.1: At baseline, MDD patients will have abnormally increased cortico-limbic connectivity.⁸⁻¹¹

Hypothesis 1.2: rTMS to DLPFC will differentially modulate this connectivity, depending on whether positively or negatively correlated regions are targeted; and one of these targets will more robustly alter this connectivity.

Hypothesis 1.3: Connectivity changes will be more pronounced in MDD patients than in controls.

Aim 2: To assess cortico-limbic network dynamics in MDD by comparing rTMS induced changes in local glucose metabolism to rTMS induced changes in distributed connectivity

Hypothesis 2.1: 20Hz will comparably increase FDG uptake at both DLPFC stimulation sites in both groups.

Hypothesis 2.2: Stimulation of the two sites will differentially impact FDG uptake at sgACC, and will have a differential impact upon the strength of connectivity between sgACC and the stimulation site.

Hypothesis 2.3: The direction and magnitude of FDG changes at sgACC will predict the direction and magnitude of the associated changes in cortico-limbic connectivity.

Hypothesis 2.4: Local and distributed changes will be altered in MDD, reflecting aberrant network dynamics.

Hypothesis 2.5: Stimulation of a control site in parietal cortex or the cerebellum will not appreciably alter cortico-limbic connectivity or metabolism.

This work will better elucidate how intrinsic networks and their dynamics are altered in MDD. It will also assess how rTMS, or other neuromodulatory strategies, create the formation of more adaptive configurations. In turn, this will pollinate future trials that optimize MDD treatments through selective targeting of intrinsic networks.

III. SUBJECT SELECTION

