Subjects will also be instructed to avoid strenuous exercise for 24 hours before the FDG-PET to minimize uptake of the radiotracer in the muscles. A fingerstick will assess the blood glucose level before FDG administration to ensure it is below the specified limit (i.e. 200 mg/dl)

An intravenous catheter will be placed and will be flushed post-injection of FDG with 0.9% saline solution. Participants will receive an intravenous bolus of 5mCi (~185 MBq) of ^{18}F Fluorodeoxyglucose (FDG) by a trained technician (specifically [name] or [name], both study staff). Injection will occur coincidentally to the onset of rTMS. Dynamic scanning will begin approximately 30 minutes after this so that dynamic changes in rCMRglu can be modeled⁶⁷ during the anticipated peak effects of rTMS. Emission data will be acquired over a 45 minute period and stored in list-mode format. Data will first be sorted in the line-of-response (LOR) space and motion correction will be applied using MRI-derived motion estimates for each individual frame. Next, data will be rebinned in the sinogram space, generating prompt and random coincidences sinograms.

rTMS procedures: rTMS will be administered with a Magstim Rapid System, using a 70 mm figure-of-eight air-cooled coil. For all sessions, 20Hz stimulation will be delivered at 110% of resting motor threshold via 75 trains of 1.2 second 20Hz rTMS (i.e., 24 pulses per train), each of which will be followed by inter-train pauses of 16.8 seconds for a total of 1800 pulses (22.5 min), for a total of 1800 pulses (22.5 min). These parameters are within recommended safety limits for rTMS⁶⁸, and replicate parameters used in Eldaief et al.¹⁴ Similar rTMS durations have been shown in other paradigms to outlast the stimulation period by anywhere from 20 minutes^{53,54} to up to 1 hour.⁶⁹ During rTMS, accurate targeting of DLPFC, or the control site, will be achieved with a frameless stereotactic optical tracking neuronavigation system (Brainsight™), which will permit real-time monitoring of coil placement and head position.⁷⁰

B. Eligibility screening and baseline questionnaires:

[figure not shown]

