Specifically, subjects will undergo simultaneous resting-state (fcMRI)/FDG-PET imaging *without* rTMS at this first visit. The baseline PET session will serve as a comparison for changes in rCMRglu following rTMS. Critically, strong evidence supports the test re-test reliability across FDG-PET scanning sessions separated in time, provided that scanning parameters remain identical.⁷¹⁻⁷⁴ Therefore, observed metabolic changes after rTMS will be attributable to the stimulation, and will be deemed unlikely to occur as a result of inherent variability across scanning sessions. Baseline fcMRI data will serve the purpose of creating functional connectivity maps from a sgACC seed. Similar to how lpIPL was designated in Eldaief et al.¹⁴, these maps will be used to establish two cortical targets for rTMS in DLPFC: one which is positively correlated to sgACC, and another which is anticorrelated to sgACC^{21,22} (**Fig 1**). After their baseline visit, subjects will return for the first of two rTMS sessions in which they will receive 20Hz stimulation to either the positively or negatively correlated left DLPFC region. They will then return for a third session in which the alternate region is stimulated (thus enabling a within-subject design). Subjects will be randomized to a given session order, and this order will be counterbalanced across subjects. It is expected that all three visits will be completed within two months from the time of enrollment. The experimental timeline for the rTMS sessions is depicted in **Fig 5**. Immediately before stimulation subjects will be rapidly scanned with resting-state fMRI *without* PET (for approx. 25 minutes). After this, they will fill out a brief (1 min) visual analog scale in which they rate sadness, anxiety, energy, concentration, happiness, anger and disgust on a scale of 0-10. They will then be taken into a room immediately adjacent to the scanner for rTMS (i.e. constituting “off-line” stimulation⁷⁵). Subjects will be injected with FDG concurrent to the onset of rTMS. After rTMS they will again complete the mood analog scale. They will then be promptly returned to the scanner room for PET/fcMRI (within ~5 min) so as to acquire BOLD data as soon as possible after rTMS.¹⁴ Dynamic PET acquisitions will correspondingly begin at this time (e.g. at approx. 30-35 min post FDG injection), and emission data will be collected for the next 45 min.

	Visit 1	Visit 2	Visit 3	Visit 4
Obtainment of Consent	X			

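### FDG is injected at rTMS onset, so the PET measure mixes uptake during and after stimulation while BOLD samples only the after-effect; the dynamic, peak-effect and simultaneity claims need correcting

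*Protocol*

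**What the plan says.** The timeline is fixed in Protocol section V.

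- **Injection.** V.A states "Injection will occur coincidentally to the onset of rTMS", and V.C repeats it: "Subjects will be injected with FDG concurrent to the onset of rTMS".
- **Stimulation.** V.A gives "75 trains of 1.2 second 20Hz rTMS (i.e., 24 pulses per train" and "inter-train pauses of 16.8 seconds for a total of 1800 pulses (22.5 min".
- **PET.** V.A: "Dynamic scanning will begin approximately 30 minutes after this so that dynamic changes in rCMRglu can be modeled", with the window described as falling "during the anticipated peak effects of rTMS". Emission data cover 45 minutes. V.C gives the start as 30–35 minutes after injection.
- **BOLD.** There are three 6-minute runs. After rTMS, subjects are back at the scanner within about 5 minutes (V.C).

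Section I says the ideal answer to a weakness of the preliminary study is to "simultaneously accrue information about changes in local nodal activity" and changes in connectivity. It presents the combined scanner as recording both after rTMS.

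Hypothesis 2.3 (section II) reads: "The direction and magnitude of FDG changes at sgACC will predict the direction and magnitude of the associated changes in cortico-limbic connectivity".

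Section VI specifies the PET variable as one normalised relative difference between the Visit 1 scan without rTMS and the post-rTMS scan.

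**The concern.** An FDG image taken late after a bolus does not show metabolism during the scan itself. It shows what has been retained since injection. Here most of the time between injection and the start of scanning is coil-on time. The measure therefore includes the on-line period, although the stimulation is described as off-line and the PET window as the period of peak rTMS effect. Nothing in the protocol acknowledges this.

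Aim 2 is at stake, because it infers network dynamics from how local metabolic change and connectivity change relate. If the two are read as concurrent after-effects, a mismatch could arise simply because they cover different periods, and would then be reported as a property of the network.

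**Working it through.** **Step 1: reproduce the stated stimulation time.** 75 × (1.2 + 16.8) s = 1350 s = 22.5 min, and 75 × 24 = 1800 pulses. Both figures agree with V.A.

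**Step 2: lay out the clock (minutes from injection).**

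- rTMS: 0 to 22.5.
- PET: 30 to 75, or 35 to 80 with the later start in V.C.
- BOLD: three runs, 18 min in all, none before 22.5.
- Stimulation as a fraction of the pre-scan interval: 22.5/30 = 75%, or 22.5/35 = 64%. Only 7.5 to 12.5 min of that interval is post-stimulation.
- V.A says after-effects outlast stimulation by 20 min to 1 hour, that is, to 42.5 or 82.5 min. With 20 min, the after-effect covers (42.5 − 30)/45 = 28% or (42.5 − 35)/45 = 17% of the PET window. With 1 hour, it covers all of it.

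**Step 3: share of retained tracer laid down during stimulation.** The documents give no kinetics, so everything here is an assumption: irreversible trapping, constant metabolism and a bolus input Cp.

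- Free tracer: dC1/dt = K1·Cp − (k2 + k3)·C1.
- Retained by time T: A(T) = ∫₀ᵀ k3·C1 dt.
- Share at T = A(22.5)/A(T). Image share = A(22.5) / mean of A(T) over the window. K1 cancels.

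Three cases were run:

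- **Reference:** constant availability, so the share at T is 22.5/T.
- **Set A:** tri-exponential input, slow rate 0.005–0.02/min; k2 0.10–0.20/min, k3 0.05–0.10/min.
- **Set B:** bi-exponential input, fast rate 0.2–0.5/min, slow rate 0.005–0.02/min, slow fraction 0.1–0.3; same k2 and k3 ranges.

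| Share from 0–22.5 min | Reference | Set A | Set B |
|---|---|---|---|
| Scan start, 30 min | 75% | 76–83% | 74–91% |
| Scan start, 35 min | 64% | 66–75% | 64–87% |
| Image, 30–75 min | 22.5/52.5 = 43% | 47–62% | 44–79% (median 59%) |
| Image, 35–80 min | 22.5/57.5 = 39% | 44–59% | 40–77% (median 56%) |
| Scan end, 75 min | 30% | 35–52% | 32–72% |
| Scan end, 80 min | 28% | 34–51% | 30–71% |

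Over sets A and B and both start times, the share is 64–91% at scan start, 40–79% over the image and 30–72% at scan end.

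**Step 4: compare the periods.** PET covers stimulation plus what follows. BOLD covers only what follows. Simultaneous acquisition does not change that.

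**The case against.** The best defence is that little in the analysis depends on the faulty sentence. Section VI defines a single normalised difference, not a time course. Section I uses simultaneity of the recording, which is true. Part of its stated motive is to learn what rTMS does at the targeted site, and tracer given at rTMS onset suits that purpose and Hypothesis 2.1. List-mode data allow late frames that carry some post-stimulation information, and the modelling rests on a cited method not available here. Section VI defines PET and BOLD outcomes separately, and section VI's control regions (motor, auditory and visual cortex) bear on non-specific effects of the coil.

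Much of this stands, and it rules out several stronger readings:

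- *That PET mainly reflects stimulation.* This is secure for the earliest frames. Over the whole image the range of 40–79% straddles one half.
- *That Hypothesis 2.3 fails.* It says predict and requires no common time window. Uptake during stimulation can predict a later connectivity change.
- *That the timing would produce a spurious patient–control difference under Hypothesis 2.4.* Injection, scanning and references are the same in both groups. A shared offset does not by itself create a difference.
- *That the Visit 1 PET reference is an error.* V.C states it and justifies it by test–retest reliability. It differs from the same-day BOLD reference, which matters for interpretation only.

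The defence does not rescue the sentence in V.A. With stimulation-period uptake already in the image when scanning begins, and the first 30 minutes unscanned, the acquisition described does not isolate metabolism at the time of the after-effect.

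**Conclusion.** The point holds as a mismatch between the protocol's claims and its own timeline. The PET measure is a mixture of stimulation-period and later uptake, and the BOLD measure is after-effect only. That the periods differ rests on the protocol's clock times plus the assumption that FDG is retained cumulatively. The percentages rest on assumed kinetics and should be read as ranges; in every case run the stimulation share of the whole image was about two fifths or more.

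The consequence is for the Aim 2 inference. Hypothesis 2.3 can be tested, but a positive result would be a relation between uptake during and shortly after stimulation and subsequent connectivity change. A PET–BOLD mismatch would not on its own be evidence about network dynamics.

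**What to change.** 1. **V.A, PET procedures:** remove or correct the claim that dynamic rCMRglu changes will be modelled at the peak of the rTMS effect.
2. **Section VI, FDG-PET data:** define the outcome as relative FDG uptake integrated from rTMS onset, covering stimulation and after-effect.
3. **Section I:** limit simultaneity to acquisition, and say that the periods represented differ.
4. **Section II, Aim 2 and Hypothesis 2.3:** word the conclusions as uptake during and shortly after stimulation predicting the subsequent connectivity change, and state that a PET–BOLD mismatch alone will not be read as network dynamics.
5. **Hypothesis 2.3 analysis:** keep the planned baseline-referenced test, because only it shows whether sgACC uptake rose or fell from the unstimulated state. Add a sensitivity analysis: sgACC uptake in the correlated-site session minus the anticorrelated-site session, against the same difference in connectivity change. With normalised post-rTMS uptake U and Visit 1 value B, (Uc − B) − (Ua − B) = Uc − Ua, so the Visit 1 reference cancels. Use U itself, since a change expressed as a ratio to B would keep B in the denominator.

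The added analysis does not remove the difference in periods and cannot replace the main test. The cost is a more modest claim and one extra analysis. Injection, stimulation, scanning and visits stay as they are.

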 3. Patients of [name] (co-investigator) who present to the MGH Depression Clinical Research Program (DCRP) with symptoms of major depression.

In the latter two cases, the PI will strongly emphasize that study participation is voluntary and that subjects' decisions to not participate will in no way affect their care with said investigator or their future care at any Partners institution.

Once identified as potentially eligible, subjects will undergo the aforementioned telephone screening/email assessments with the PI to further delineate their eligibility.

IV. SUBJECT ENROLLMENT

- A. Subjects will be randomized as to the order of the TMS sessions they undergo (there are two types of sessions in which one of two sites on the prefrontal cortex is stimulated). The order of these sessions will be counterbalanced across subjects. In other words, we will alternate between the two types of sessions and will have equal numbers of subjects having undergone a particular order of sessions. This will allow us to account for order effects.

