Study procedures will first consist of completion of study questionnaires followed by experimental procedures. In order to ensure eligibility to participate, all subjects will complete a SCID and HDRS rating scale. These will confirm the existence/absence of major depression and the absence of comorbid psychiatric conditions. Other exclusionary criteria will be screened via non-structured clinical interviews. A subject's eligibility for safely receiving rTMS, PET and fMRI will be assessed by filling out the appropriate screening forms (see attachments). All of these procedures will be performed by [name] (PI) who is trained in administering these instruments and screening forms. Finally, women of childbearing age will undergo a STAT quantitative serum hCG to ensure that they are not pregnant.

C. Aim 1 and 2 Experimental Procedures

50 subjects (25 MDD patients and 25 matched controls) will each undergo three experimental visits. In addition, of these subjects a subset (no more than five) will be given the option to undergo a fourth experimental visit. During the first study visit, consent will be obtained. Following this, subjects will be assessed for eligibility by

Fig 5.

Experimental timeline. Baseline fMRI/PET done on visit 1. Subjects return days later for 2-3 more visits in which they have fMRIs before rTMS and fMRI/PET afterwards.

screening procedures mentioned above. If they are considered eligible, they will undergo a baseline scan during this visit.

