Experimental Controls: To ensure that the effects of rTMS are specific to the cortico-limbic systems investigated, we will construct three extra-network seed regions: primary motor cortex (M1), primary auditory cortex (A1) and primary visual cortex (V1). A lack of rTMS induced changes in rCMRglu in these regions; and a lack of rTMS induced changes in inter-hemispheric functional connectivity between these regions, will corroborate network specific effects. To ensure that the effects of rTMS are not the result of inherent variability of connectivity between two fMRI acquisitions separated in time, we will compare *pre*-rTMS fMRI scans between the two stimulation sessions (correlated and anticorrelated). A lack of significant variability between these will argue that changes were caused by rTMS (identical controls were used in Eldaief et al.¹⁴)

Rating scales: Paired t-tests will compare mood analog scale ratings before and after rTMS to assess the possibility that stimulation of cortico-limbic networks confers transient mood altering effects.

VII. RISKS AND DISCOMFORTS

Risks attributable to MRI: There are no known or foreseeable risks associated with conventional MRI procedures except to those people who have electrically, magnetically or mechanically activated implants (such as cardiac pacemakers), or those who have cerebrovascular clips. Participants will therefore be screened very carefully (with a standardized MRI screening form-see attachment) to exclude the possibility that they have any such devices and/or implants, and will be excluded from participation in the event that they do. There are no known additional risks associated with functional MRI, and the functional MRI systems to be employed have been approved by the FDA and will be operated within the standards reviewed and accepted by the FDA. All studies will specifically adhere to these FDA approved safety levels for the Siemens system. These safety parameters include static magnetic field, time varying magnetic fields (dB/dt), specific absorption rate (SAR), and acoustic noise levels. Subjects will be informed about minimal risks of routine high magnetic field and non-ionizing RF radiation involved in MR imaging. Still, an MRI might be uncomfortable to a subject due to the risk of a) claustrophobia; b) boredom from lying still for an extended time or c) being perturbed by scanner noise.

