In terms of seizures, all rTMS sessions will be conducted by the PI ([name]) who is (1) a board certified neurologist, (2) has been trained in the safe and efficient administration of TMS (through a course offered at the Berenson-Allen Center for Non-Invasive Brain Stimulation at the Beth Israel Deaconess Medical Center) and (3) is trained in basic life support and in the recognition and treatment of convulsions, syncope and other medical/neurological emergencies. In addition, a fully equipped and regularly checked crash cart will be available at all sites where TMS stimulation will occur. This emergency equipment includes oxygen supply, IV line supplies, and emergency medications (e.g. benzodiazepines) in the event of a convulsion. Therefore, should any complication occur, rapid medical coverage for the subject will be provided, followed by Emergency Room care if appropriate. We will also monitor patients in detail during and after delivery of rTMS, using an approach drawn directly from suggested guidelines.⁶⁸ Notably, there is not expected to be an increase in the risk of seizures with stimulation of the control site. In fact, stimulation of the cerebellum is much less likely to result in seizure induction. Other measures to minimize risks from TMS are listed in **Table 2**.

Risk Associated with TMS	Measures taken to prevent/minimize this risk
20-40% of subjects experience MILD headaches or neck pain	Care will be taken to administer stimulation in a comfortable neck position and to avoid unnecessary stimulation of neck/scalp muscles.
TMS produces a loud clicking sound which may cause tinnitus or rarely short-term hearing loss	Subjects will be given earplugs, which, in animal and human studies, proven effective in preventing the risk of hearing disturbance due to TMS.
TMS could induce short-term changes in memory, attention and other cognitive functions	This is a theoretical risk, as none of the safety studies conducted has found such side effects.
Acute psychiatric effects such as mania and delusions have been described in patients with medically refractory depression or bipolar disorder who received rTMS. This seems to be a rare complication of rTMS (incidence <0.15% of patients).	Mania and delusions arising from TMS have not been described in purely schizophrenic cohorts, e.g. those without a comorbid affective disorder. Subjects will undergo a brief rTMS side effects questionnaire after rTMS to assess for these rare effects.

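### Change in PET from an unstimulated first-visit scan cannot be attributed to rTMS, because visit order and the non-specific effects of receiving rTMS change with it

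*Protocol*

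**What the plan says.** Section I names rTMS-induced change in rCMRglu at the DLPFC stimulation sites and in sgACC among the primary outcomes. Section V.C fixes the comparator: "The baseline PET session will serve as a comparison for changes in rCMRglu following rTMS". The Fig 5 caption gives the order: "Baseline fMRI/PET done on visit 1. Subjects return days later for 2-3 more visits".

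Only the order of the two active DLPFC sessions is randomised and counterbalanced. In IV.A, "there are two types of sessions in which one of two sites on the prefrontal cortex is stimulated". No sham session is described.

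For the stimulation visits V.C says: "Subjects will be injected with FDG concurrent to the onset of rTMS". Section V.A gives the stimulation time as 22.5 minutes. For visit 1, V.C says only that fcMRI and FDG-PET are done together without rTMS.

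V.C then argues that FDG-PET is reliable on retest, "provided that scanning parameters remain identical", and concludes that "observed metabolic changes after rTMS will be attributable to the stimulation". Section VI tests each post-rTMS scan against the baseline scan with a paired t-test. It also plans comparisons of rCMRglu change between rTMS conditions and between MDD patients and controls.

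**The concern.** The step from reliability to attribution does not follow, for two reasons.

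- Retest reliability describes how closely like sessions agree. It does not exclude a systematic difference between a first scan, on the day of consent and screening, and a later scan.
- The sessions are not alike. Uptake at the later visits takes place during rTMS, which brings noise, scalp sensation and possibly arousal, whichever target is stimulated. Table 2 in section VII says: "TMS produces a loud clicking sound which may cause tinnitus or rarely short-term hearing loss".

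Every baseline-versus-post PET contrast inherits this. Hypothesis 2.1 (raised uptake at both DLPFC sites) rests wholly on such contrasts, as does any statement that sgACC metabolism rose or fell after stimulation of one site. A non-specific regional shift would be reported as a stimulation effect on a primary outcome.

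**Working it through.** **Inputs.** Section III.D gives a planning change of 5.3% with SD 2.77%, alpha 0.05, power 90%, and 25 subjects per group. The tests below are taken as two-sided, which the protocol does not state. The size of a non-specific shift is not given and is assumed.

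**The plan's own figure.** The standardised effect is 5.3 / 2.77 = 1.91. The exact noncentral-t calculation gives 6 subjects for a paired test and 7 per group for an unpaired test. The protocol states 7 and 5 respectively. Each is within two subjects, and the gap does not matter here because 25 are recruited.

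**What the two contrasts estimate.** Let s be the shift from visit 1 to a later rTMS visit that does not depend on the target, and let a and b be the true effects of stimulating the two sites.

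- Post-rTMS minus baseline: a + s (or b + s). Nothing in the design separates the two terms.
- Difference between the two changes: (a + s) − (b + s) = a − b. The shared visit-1 scan and the common shift both cancel.

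**Rejection probability with no true effect (a = 0).** For n = 25 the paired test has 24 degrees of freedom, a critical value of 2.064 and noncentrality s × √25 / SD. For s = 2% and SD 2.77% this is 2 × 5 / 2.77 = 3.61, which gives 93%.

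| Assumed shift | SD 2.77% | SD 3.92% | SD 5.54% |
|---|---|---|---|
| 0 | 5% | 5% | 5% |
| 1% | 41% | 23% | 14% |
| 2% | 93% | 69% | 41% |
| 3% | >99% | 96% | 74% |

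The two larger SDs are assumptions: 2.77 × √2 = 3.92 and 2.77 × 2 = 5.54.

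**Simulation.** In 20,000 runs with one baseline and two post-rTMS scans (SD of change 2.77%), a common shift of 2% was declared an effect at both sites in 88% of runs. The between-session contrast rejected in 4.9% to 5.2% of runs for shifts from 0 to 3%.

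**Do the planned safeguards close the gap?**

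- *Normalised rCMRglu (VI).* If this is intensity normalisation, it removes a global shift but not a regional one.
- *M1, A1 and V1 (VI, Experimental Controls).* The protocol would take "A lack of rTMS induced changes in rCMRglu in these regions", together with stable connectivity there, as support for network specificity. A shift confined to prefrontal or limbic regions would pass unseen, and a non-significant result is not evidence of no change.
- *Comparison of pre-rTMS scans between sessions (VI).* This uses fMRI only. No pre-rTMS PET is taken at the stimulation visits.
- *Control site (Hypothesis 2.5).* The optional fourth visit covers at most five subjects, and its use for the control site is inferred. With n = 5 and SD 2.77% the 95% half-width is 2.776 × 2.77 / √5 = 3.4 percentage points, and power to detect a 2% shift is 24%.

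**The case against.** The best defence is that the protected comparison is already in the plan. Section VI compares rCMRglu changes across rTMS conditions, Hypothesis 2.2 asks that question at sgACC, and the order of the sites is counterbalanced. This stands. A reader might infer that the trial has no sound causal PET contrast, and the protocol does not support that. The planned MDD-versus-control comparison also cancels a shift common to both groups, though not one that differs between them.

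A reader might also infer that the visit-1 scan was silent, in another room, or without a preceding scan. The text does not say so. The visit-1 uptake setting is not described and the figure is not shown, so only the absence of rTMS and the fixed visit order are certain. Table 2 also provides earplugs, which reduce the auditory component but need not remove it.

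Nor is the A1 check worthless. If clicks raise A1 metabolism, the check fails, which works against a false claim of specificity, although for a reason unrelated to the network. M1 and V1 remain.

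Lastly, the table above is not evidence that bias exists. Nothing in the protocol suggests a shift of 2%, and the planning SD comes from a cited motor-cortex study. All of this limits the size of the claim. None of it rescues the attribution sentence, which is unqualified and covers all metabolic changes after rTMS.

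**Conclusion.** The point holds for every baseline-versus-post PET contrast, and so for Hypothesis 2.1 and for one-site changes at sgACC. In these contrasts stimulation is fully confounded with later visit and with the non-specific experience of rTMS, and the reliability argument does not repair that. The contrast between the two sessions is protected against a shift common to both.

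The size is conditional. With 25 subjects and no true effect, an assumed 2% shift (under half the 5.3% planning change) would be called an rTMS effect with probability 93%, 69% or 41% across the three SDs. Whether such a shift exists is unknown.

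**What to change.** 1. Delete or qualify the attribution sentence in V.C.
2. Base causal PET claims, at each DLPFC site and at sgACC, on the contrast between the two rTMS sessions that section VI already plans.
3. Report change from visit 1, including Hypothesis 2.1, as not separable from visit and non-specific effects.
4. Apply the M1/A1/V1 check to the between-session contrast as well.

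This changes analysis priority and wording only, with no new scans. The price is that an effect common to both sites cancels and can only be described. Scalp sensation may also differ somewhat between the more medial and the more lateral target, so the contrast is not perfectly matched.
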